2.13 Planned Analyses, Sample Size, and Stopping Rules

The Sponsor will conduct the following analyses corresponding to the study objectives and prepare a clinical study report. Where appropriate, descriptive statistics will be used.

Primary Objective:

1. Workflow feasibility:

For each subject, workflow feasibility will be judged as successful or not based on the following criteria:

Treatment for an individual subject will be deemed NOT feasible if:

- Total treatment time on table is greater than one hour OR
- A delay in study treatment of more than 7 business days from simulation to treatment occurs related to the investigational device (excluding delays due to patient or facility factors not related to the study treatment)

2. Toxicities of treatment:

All toxicities will be tabulated and summarized. Toxicities that are possibly, probably, or definitely related to FLASH radiotherapy will be used for the assessment of toxicity of the FLASH treatment.

Note: A dose-limiting toxicity (DLT) is defined as a Grade ≥ 3 toxicity attributed as possibly, probably, or definitely related to FLASH radiotherapy. The number of DLTs will be monitored through the duration of the study and will be used as a criterion in the Stopping Rules (see section 2.13 for a Stopping Rule related to DLT.)

Secondary Objective:

3. Pain relief:

As discussed above in section 2.8.6 patient reported pain score (overall) at baseline and post-treatment (Day 15, Month 1, Month 2, Month 3, long-term) will be assessed using the Brief Pain Inventory (BPI) short form questionnaire. Patient reported pain score for each treated site will be assessed using the Treated Sites Pain questionnaire.

The BPI short form questionnaire was selected to permit the results of this study to be compared with prior published results using this instrument [10].

Per the methodology of Hartsell, et al. [10]: The worst pain score in the BPI short form will be used to assess treatment response; a complete response will be defined as having no pain at 3 months after radiation therapy; a partial response will be defined as a pain score that is at least two points lower than the initial response; a stable response

will be defined as a one-point change in pain score in either direction; a progressive response will be defined as a pain score that is at least two points higher than the initial score. The same analysis will be applied to the individual sites treated by FLASH, as assessed by the questionnaire with the four-item subset of the BPI questionnaire.

Per the methodology of Chow et al., flare in bone pain due to radiation will be assessed using the Pain Flare questionnaire administered on Day 1 - Day 11. Pain flare is defined as either of the following: a minimum of a two-point increase in the worst pain score for the treated site without a reduction in analgesic intake; or a 25% or greater increase in analgesic intake based on daily oral morphine equivalence without a reduction in the worst pain score. If the worst pain score before treatment was nine or ten, the criteria for pain flare were met if the follow-up worst pain score was ten and reported as worse than the worst pain before treatment with no decrease in analgesic intake. To distinguish pain flare from progression of pain, the worst pain score and analgesic intake had to return to baseline levels during the 11-day (Day 1 - Day 11) time period. Consistent with the Chow study, we will document use of steroid medication.

Data on use of pain medication will be collected and changes in pain medication use will be evaluated between baseline, during each of the first 10 days after treatment, and follow-up visits (Day 15, Month 1, Month 2, Month 3). The percentage of patients requiring narcotic, non-narcotic analgesics, and no pain medications will be assessed and compared to literature values from prior clinical trials.

Sample Size:

For this feasibility study, a sample size of up to 10 patients will apply.

Stopping Rules:

Triggering of a stopping rule will result in a cessation of enrollment and in a review of the study data by the Cincinnati Cancer and Blood Disease Institute Data Safety Monitoring Board and Study Committee (PI and co-investigators).

The study will be stopped if any of the following occurs:

- 3 subjects experience a dose limiting toxicity (DLT) (see section 2.13 for definition of DLT)
- 3 subjects have time on the treatment table >1 hour
- 3 subjects have a delay in study treatment of more than 7 business days from simulation to treatment related to the investigational device (excluding delays due to patient or facility factors not related to the study treatment.)
- A major device malfunction in dose delivery (as indicated by the dose monitoring system). This includes potential recordable or reportable medical events under the Ohio Department of Health classification.

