2.5 Outcome Measures

The outcome measures corresponding to the study objectives are as follows:

Primary Objective Outcome Measures:

1. Workflow feasibility:

- Patient time on the treatment table
- Delays in study treatment related to the investigational device (excluding delays due to patient or facility factors not related to study treatment)

2. Toxicities of treatment:

- Toxicities that are possibly, probably, or definitely related to FLASH radiotherapy
Toxicities will be classified per CTCAE¹ version 5.0

Secondary Objective Outcome Measures:

3. Pain relief:

- Patient reported pain score overall and specifically for treated sites
- Use of pain medication

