2.8.5 FLASH Radiotherapy Delivery (Day 1)

The treatment plan will be transferred from the ARIA Oncology Information System (Varian, Palo Alto, CA; ARIA is used without modification to the present 510(k) clearance) to the FLASH enabled ProBeam Proton Therapy System console for FLASH radiotherapy delivery. Subjects will be positioned on the treatment couch as determined at the time of their simulation visit. Image guidance will be used to verify that the target is in the correct position for treatment. The treatment will be carried out for up to 3 treatment sites for each subject, depending on the total number of painful bone metastases in limb bones (excluding feet, hands, wrists) to be treated.

On the day of treatment, but before start of treatment, the following baseline data will be recorded: patient reported pain score overall and specifically at each treated site (see section 2.8.6 for questionnaires to be used); subject evaluation (use of pain medication (including steroid medications), performance status, photographs of skin and any physical findings on examination involving the skin or other normal tissue in the treatment site(s)).

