3.1 Risks and Mitigations

A risk with any modality of radiation therapy, including FLASH radiotherapy, is harm to normal tissues that are included within the treatment volume. In the case of FLASH radiotherapy, the side effects are expected to have the same spectrum of symptoms or physical findings that can result from conventional photon radiotherapy at conventional dose rates. Preclinical data suggests that FLASH radiotherapy may result in less toxicity to normal tissues.

Potential risks/toxicities in this clinical study:

- Skin
 - Red skin
 - Weeping of skin
 - Ulceration of skin
 - Necrosis
 - Fibrosis
 - Hyper- or hypopigmentation
 - Hair loss in the treated area
- Swelling in the extremities (lymphedema)
- Potential damage to other normal tissues in the radiation field, including to muscle, nerve, and/or bone
- Insufficient pain relief
- Fracture at the metastasis site
- Decreased blood cell count
- Radiation related secondary malignancy

Patients who are pregnant or nursing are excluded from the study because radiation treatment can pose risk to an unborn or nursing child.

The machine and patient specific QA processes outlined in section 2.8.4 are in place to verify that the correct dose is delivered as prescribed.

In the event of an interrupted FLASH treatment (as sometimes can occur with standard dose rate radiation treatment delivery), treatment may be resumed and the system will correctly execute the remainder of the plan such that the full absorbed dose of 8 Gy will be delivered to the target volume. If a spot is partially delivered, the system automatically recalculates the maximum allowed beam current to complete the remaining monitor units for that spot. This may reduce the dose rate for the remainder of the field. The potential normal tissue sparing benefit of the FLASH dose rate may be less. However, treatment can be completed likely

without any reduced effect in treating the tumor. Based on reliability testing, treatment interruption is unlikely to occur.

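### The per-subject feasibility rule in section 2.13 can score a treated subject as feasible when the device left the planned delivery incomplete or malfunctioned in dose delivery, provided neither time limit is exceeded

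*Combined protocol and SAP*

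**What the plan says.** Section 2.13 makes feasibility a yes/no verdict for each subject: "workflow feasibility will be judged as successful or not based on the following criteria". The rule itself begins "Treatment for an individual subject will be deemed NOT feasible if", and two grounds for a negative verdict follow. One is "Total treatment time on table is greater than one hour OR"; the other is "A delay in study treatment of more than 7 business days from simulation to treatment occurs related to the investigational device", with patient and unrelated facility factors set aside. Section 2.5 and the synopsis name the same two domains as outcome measures: time on the table, and "Delays in study treatment related to the investigational device (excluding delays due to patient or facility factors not related to study treatment").

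Delivery problems are dealt with in other places:

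- Section 2.8.5: "The treatment will be carried out for up to 3 treatment sites for each subject".
- Section 2.10: every problem with FLASH delivery, including device failure, is documented and reported to the sponsor.
- Section 2.13, stopping rules: the list ends with "A major device malfunction in dose delivery (as indicated by the dose monitoring system"). A single event is enough. The effect is that enrollment ceases and the data are reviewed.
- Section 2.14: delivery log files are among the data that may be collected.
- Section 3.1: after an interruption, "treatment may be resumed and the system will correctly execute the remainder of the plan", possibly at a reduced dose rate. Interruption is described as unlikely.

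**The concern.** The first primary objective is whether FLASH delivery works in a clinical setting, yet the rule that scores it never asks whether the planned delivery took place. Suppose a subject has three planned sites and a device fault leaves the third untreated or only partly treated. If the session stayed within the hour and began on time, the rule as written gives no reason to call that subject not feasible.

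The stopping rules show the mismatch. Two of the four (table time, delay) mirror the feasibility grounds, and the toxicity rule mirrors the other primary objective. Only the malfunction rule has no counterpart in a primary outcome. One such event can halt enrollment while the subject in whom it occurred is still reported as a feasibility success.

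At stake is how the main descriptive result reads. In a cohort this small, one mis-scored subject is visible in the reported proportion.

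**Working it through.** The plan gives no calculation to reproduce: the sample size of up to 10 (section 2.13) is stated without a target rate, threshold or power. The check is therefore of the decision rule itself.

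**1. Enumerate the rule.** Let T = table time over one hour, D = device-related delay of more than 7 business days, and I = planned delivery incomplete at one or more sites for a device reason, or a malfunction meeting the stopping rule.

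Current rule: not feasible if T or D. Rule with a third ground: not feasible if T or D or I.

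| T | D | I | Current rule | With third ground |
|---|---|---|---|---|
| no | no | no | feasible | feasible |
| no | no | yes | **feasible** | **not feasible** |
| no | yes | no | not feasible | not feasible |
| no | yes | yes | not feasible | not feasible |
| yes | no | no | not feasible | not feasible |
| yes | no | yes | not feasible | not feasible |
| yes | yes | no | not feasible | not feasible |
| yes | yes | yes | not feasible | not feasible |

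One of the 8 combinations changes: delivery fails, but both time limits are met.

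**2. Look for another route to a negative verdict.** Section 2.10 leads to a report. The malfunction stopping rule leads to a halt and a data review. Section 3.1 leads to resumption. None of them reclassifies a subject.

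**3. Effect on the result.** One subject is 1/n of the proportion. With n = 10 that is 1/10 = 10 percentage points; with fewer treated subjects it is more. Exact (Clopper-Pearson) 95% intervals, for scale:

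- 10/10: 69.2% to 100%
- 9/10: 55.5% to 99.7%
- 8/10: 44.4% to 97.5%

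These describe the precision of any proportion in 10 subjects. They do not measure how often the gap is met.

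**4. Chance of meeting the case.** The documents give no rate of incomplete delivery, so the per-subject rate q is an assumption. The chance of at least one such subject among 10 is 1 − (1 − q)^10:

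| Assumed q | At least one in 10 |
|---|---|
| 1% | 1 − 0.99^10 = 9.6% |
| 2% | 1 − 0.98^10 = 18.3% |
| 5% | 1 − 0.95^10 = 40.1% |
| 10% | 1 − 0.90^10 = 65.1% |
| 20% | 1 − 0.80^10 = 89.3% |

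These are upper figures for the mis-scored case, because some incomplete deliveries would also breach a time limit and be caught. Given the wording of section 3.1, the lower rows are the more plausible ones.

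**The case against.** The best defence is that the endpoint is labelled workflow feasibility, is defined in the same terms in the synopsis, section 2.5 and section 2.13, and leaves device reliability to device reporting and the stopping rules. In one respect those are stricter: one major malfunction halts enrollment, whereas the table-time and delay rules each need 3 subjects. Section 3.1 also expects interruption to be unlikely and gives a route to full dose. This is why the case should be rare. It does not alter the verdict for a subject in whom the case occurs. The malfunction rule also acts on the study rather than the subject, and covers only events classed as major.

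A second defence is that the delay ground may already reach part of this. If study treatment means all planned sites, a site still untreated more than 7 business days after simulation for a device reason could count as delayed. That reading is open, but section 2.13 does not say whether the clock stops at the first site or the last, and a partly delivered field fits neither reading cleanly.

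Two stronger conclusions are tempting:

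- A reader might infer that the rule rewards failure, because an aborted delivery shortens table time. The documents do not support this in general. Section 2.3 says a whole fraction can be given in under a second, so abandoning a field saves almost no time, and handling a fault would tend to lengthen the session. Only skipping later sites could shorten it.
- A reader might infer that the study could report 10/10 feasible with no completed delivery. The per-subject rule alone allows it, but the malfunction stopping rule would probably intervene well before then.

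**Conclusion.** The concern holds in a limited form. As written, section 2.13 returns the wrong verdict for a treated subject with a device-related incomplete delivery, or a stopping-rule malfunction, when both time limits are met. The plan states its criteria explicitly and they give this result, so it is more than missing detail.

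The size is modest. Each such subject moves the proportion by 10 percentage points at n = 10. Because the plan is descriptive and sets no success threshold, that shift crosses no planned decision boundary. How often it would happen cannot be known from the documents; the rates in the table are assumptions.

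The conclusion assumes that the two listed grounds are exhaustive, as the section's wording indicates, and it concerns only subjects who received some FLASH treatment and stay in the count. It should be corrected, but it does not undermine the study: the malfunction stop, the device reports and the clinical study report remain as safeguards.

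**What to change.** In section 2.13:

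1. Add a third not-feasible ground: planned delivery not completed at every planned FLASH site, for a device-related reason, within the same 7-business-day window from simulation that the delay ground uses; or any event that meets the device-malfunction stopping rule. Using the same window keeps the two grounds consistent. A requirement tied to the Day 1 session would fail a site completed within a delay that the existing ground tolerates. The window is for scoring only and says nothing about how or when an incomplete delivery should be managed.
2. State that the delay ground applies to each planned site.
3. Add a table of sites planned, completed without interruption, completed after interruption, and not completed. Sites completed after interruption would still count as feasible but would be visible.

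Section 2.5 and the synopsis need a matching line.

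The cost is a few sentences and one table. The section 2.10 device reports are already required and supply most of the data; the delivery logs can add to them where collected, since section 2.14 lists these only as data that may be collected. The drawback for the sponsor is a possibly less favourable feasibility count. No dose, schedule or clinical management changes.

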2.2 Protocol Summary

2.2.1 Protocol Synopsis

Study Title	Feasibility study of FLASH radiotherapy for the treatment of symptomatic bone metastases
Study Description	This clinical study is designed as a prospective feasibility study to assess the workflow feasibility of FLASH radiotherapy in a clinical setting, toxicities, and pain relief following treatment of painful bone metastasis(-es) in the extremities.
Objectives	
Primary Objective:
 
 1. Assess workflow feasibility of FLASH radiotherapy in a clinical setting 2. Assess toxicities of treatment 
Secondary Objective:
 
 3. Assess pain relief at the treated site(s)
Outcome Measures	
Primary Objective Outcome Measure:
 
 1. Workflow feasibility: 
 • Patient time on the treatment table • Delays in study treatment related to the investigational device (excluding delays due to patient or facility factors not related to study treatment) 2. Toxicities of treatment: 
 • Toxicities that are possibly, probably, or definitely related to FLASH radiotherapy 
Secondary Objective Outcome Measures:
 
 3. Pain relief: 
 • Patient reported pain score overall and specifically for treated sites • Use of pain medication
Study Population	The study population will consist of up to 10 patients with painful bone metastasis(-es) in the extremities who are treated using FLASH radiotherapy to 1-3 sites. Patients at least 18 years of age will be considered regardless of race or gender.
Description of Study Intervention	Subjects will be treated for painful metastases in the extremities (limbs, excluding feet, hands, wrists) using FLASH radiotherapy. The FLASH enabled ProBeam Proton Therapy System, which delivers proton radiation at a FLASH dose rate, will be used for subject treatments.
Description of Sites Enrolling Participants	The study will be carried out at 1 investigational site with a ProBeam Proton Therapy System that is modified to deliver proton radiation at a FLASH dose rate.

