2.8.1 Screening, Informed Consent, and Baseline Evaluation

Screening, Informed Consent

Patients will be informed about the study primarily by radiation oncologists and their staff. The results of the screening process will be compiled by the investigational site and the investigator will determine whether the patient meets the eligibility criteria. Patients interested in participating in the study will be asked to read, understand and sign the Informed Consent document, consistent with institutional practices. Patients who meet all eligibility criteria and sign consent may proceed onto the study.

Note that during the study, subjects will be informed of new information and asked to sign a revised Informed Consent document when requested by IRB, the Principal Investigator, or the Sponsor.

Each subject will be given a unique study identification code; the link between the identification code and the subject's identity will be maintained by the Principal Investigator. The code will be entered onto each subject's case report forms and other study records.

Replacement of subjects

Only subjects who are treated on this study protocol will be counted towards the study patient limit.

Subjects who sign the informed consent form and subsequently withdraw, or are withdrawn, from the study prior to receiving the FLASH radiotherapy will not be counted towards the study patient limit and will be replaced.

Subjects who sign the informed consent form, receive the FLASH radiotherapy, and subsequently withdraw, or are withdrawn from the study, will be counted towards the study patient limit and will not be replaced.

Baseline Evaluation

Subject characteristics will be recorded, including age, gender, performance status, history of medical comorbidities or autoimmune disorders, diagnosis date, prior cancer-directed treatments. Tumor characteristics will be recorded, including histology, anatomic location of the original primary tumor and the anatomic location of treatment site(s), target lesion size, target lesion extent of bone circumferential involvement (if available), metastasis type (i.e., lytic, blastic, mixed). Subject evaluation data will be recorded: review of pain medications (including steroid medications), performance status, photographs of skin and any physical findings on examination involving the skin or other normal tissue in the planned treatment site(s).

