2.8.2 CT-based Simulation

Simulation imaging is performed as part of standard of care in order to develop the radiation treatment plan. During the simulation procedure, the subject is placed on the CT simulator couch in a stable and reproducible position suitable for targeting the metastatic lesion(s). Immobilization devices such as a Vac-Lok bag will be used for all subjects to aid in immobilizing the target site(s) and for reproducing the subject's positioning at the time of treatment. A CT scan will be obtained through the areas of interest and used for radiotherapy planning.

Adequate radiotherapy coverage of the target lesion(s) will be assessed using this CT during the treatment plan selection process (see section 2.8.3). This assessment will be carried out for each of the planned FLASH treatment sites (up to 3 FLASH treatment sites for each subject). Subjects who cannot be treated using the available pre-defined treatment field sizes (see inclusion criteria) will be removed from the study and replaced.

Women of childbearing age must have a negative pregnancy test at the time of CT simulation. If the pregnancy test is positive, the subject will be removed from the study and replaced. It is standard of care at the investigational site to evaluate pregnancy status for women of childbearing age at the time of CT simulation.

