3.3 Study Population

The study population will consist of up to 10 patients with painful bone metastasis(-es) in the extremities who will be treated using FLASH radiotherapy to 1-3 sites. Patients at least 18 years of age will be considered regardless of race or gender.

4 Description of Device

The ProBeam Proton Therapy System is an FDA Class II and an EU MDR Class IIb medical device that incorporates a superconducting cyclotron that produces 250 MeV protons. A degrader followed by an energy selector is used to vary the proton beam energy. The adjusted energy, current, and size of the proton beam is sequentially channeled to a treatment room using a beamline. A treatment room is equipped with a robot-mounted treatment table and, in many installations, a gantry to allow the proton beam to be applied to a patient from all directions.

The FLASH enabled version of the ProBeam Proton Therapy System is being developed under the regulations pertaining to 21CFR 820. This FLASH enabled device is a modified and tested ProBeam Proton Therapy System with the ability to deliver pre-defined high dose rate plans of fixed field sizes and total dose, using a specific treatment workflow. These pre-defined plans will be delivered with a minimum dose rate to the target volume of 40 Gy/s and a maximum fluctuation of 10% around the mean.

No changes are anticipated to the device during the clinical investigation.

5 Monitoring Procedures

The study will be monitored according to US FDA regulations and Good Clinical Practices.

The study monitor is:

[name]
[contact]

The Sponsor's medical monitor is:

[name] (Radiation Oncologist)
[contact]
[REDACTED] (voicemail) or [REDACTED] (mobile)

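### The feasibility score in section 2.13 has no NOT-feasible ground for an eligible, simulated subject whom the device could not treat and who leaves by business day 7 with at most one hour on the table

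*Combined protocol and SAP*

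**What the plan says.** Section 2.13 sets a binary score: "For each subject, workflow feasibility will be judged as successful or not based on the following criteria". Two grounds make a subject NOT feasible. The first is "Total treatment time on table is greater than one hour". The second is "A delay in study treatment of more than 7 business days from simulation to treatment occurs related to the investigational device", with patient factors and unrelated facility factors carved out. Failure to deliver the treatment at all is not listed, and no analysis set is named for the score.

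The rest of the protocol bears on who is scored:

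- **Population.** The synopsis (2.2.1) describes "up to 10 patients with painful bone metastasis(-es) in the extremities who are treated using FLASH radiotherapy to 1-3 sites". Section 3.3 likewise refers to patients "who will be treated using FLASH radiotherapy to 1-3 sites".
- **Replacement.** Under section 2.8.1, consented subjects who leave "prior to receiving the FLASH radiotherapy will not be counted towards the study patient limit and will be replaced". The cause of leaving makes no difference.
- **Eligibility failures found at simulation.** Section 2.8.2 states: "Subjects who cannot be treated using the available pre-defined treatment field sizes (see inclusion criteria) will be removed from the study and replaced". For pregnancy it states: "If the pregnancy test is positive, the subject will be removed from the study and replaced".
- **Outcome measure.** Sections 2.2.1 and 2.5 list table time and device-related treatment delays, with no 7-day limit.
- **Records.** Section 2.10 requires device problems to be documented, 2.11 covers deviations and other study problems, and 2.12 requires the reason for leaving.
- **Stopping rules.** The delay rule in 2.13 repeats the 7-business-day condition for 3 subjects. A separate rule covers a major malfunction in dose delivery.

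**The concern.** A feasibility score for a new device should count against the device those cases in which it could not do the job. Here the worst workflow result, no treatment, has no ground of its own. It can enter only if it is read as a delay or if table time runs over an hour.

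The route is credible. Section 2.8.4 requires a check of FLASH dose and dose-rate constancy on the day of treatment, before the subject is treated, and the protocol does not say how a failed check is scored. These patients are in pain, and section 2.3 expects conventional off-study treatment to be very similar, so a subject might well leave rather than wait. Replacement then fills the place.

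At stake is a descriptive primary result that could look more favourable than the device's performance warrants. No hypothesis test or success threshold depends on it.

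**Working it through.** **Inputs.** The two grounds and the unit of scoring come from section 2.13. The limit of up to 10 treated subjects comes from 2.13 and 2.8.1. The plan gives no derivation of 10, no target rate and no feasibility proportion, so there is no figure to reproduce. Let k be the number of eligible, simulated subjects left untreated because of the device who are gone by business day 7 with at most one hour on the table. The documents give no value for k; it is an assumption throughout.

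**Step 1: apply the grounds.** Suppose the day-of-treatment check fails and the subject leaves on business day 3 after simulation.

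- Table time: not over one hour, so the ground is not met.
- Delay: 3 business days have elapsed at exit, fewer than 7, and no treatment date closes the interval. The ground is not met on its face.

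**Step 2: ask who is scored.** With no analysis set named, three readings are open.

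- A. The subject is omitted, because the population is described as treated patients and the place is refilled. This is the most likely reading.
- B. Treatment that never happens is taken as a delay without end, so the subject is NOT feasible. The text neither says this nor rules it out.
- C. The subject is one of those judged, meets no ground, and counts as a success. This is the least plausible reading, because both grounds presuppose a treatment.

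**Step 3: compare neighbouring cases with the same device fault.**

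| Course | Score under 2.13 |
|---|---|
| Stays, treated on business day 8 | NOT feasible |
| Stays on study untreated past day 7 | Could be caught by the delay ground |
| Over one hour on the table, then no delivery | Could be caught by the table-time ground, if that covers an attempt without delivery |
| Leaves by day 7, at most one hour on the table | Most likely not scored |

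**Step 4: illustrate the size.** Take 10 treated subjects, all feasible. Reading A gives 10/10. Reading C gives (10 + k)/(10 + k). Scoring the subject NOT feasible, as in reading B or after the fix, gives 10/(10 + k).

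| Assumed k | A: omitted | C: success | NOT feasible |
|---|---|---|---|
| 0 | 10/10 = 100% | 10/10 = 100% | 10/10 = 100% |
| 1 | 10/10 = 100% | 11/11 = 100% | 10/11 = 90.9% |
| 2 | 10/10 = 100% | 12/12 = 100% | 10/12 = 83.3% |
| 3 | 10/10 = 100% | 13/13 = 100% | 10/13 = 76.9% |

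At k = 1 the difference is 100 − 90.9 = 9.1 percentage points. At k = 0 there is none.

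**Step 5: check the stopping rules.** The delay rule uses the same condition as the second ground and so carries the same ambiguity. The malfunction rule stops enrollment and brings a data review, but it does not score the subject, and it does not clearly reach a check that fails before any delivery.

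**The case against.** The strongest reply is that the protocol does not lose the event. The outcome measure in section 2.5 is device-related delay with no threshold, so a failed check that puts off treatment is arguably a recorded delay even if the subject then leaves. Sections 2.10 to 2.12 would document the device problem and the exit, and a major malfunction in dose delivery leads to review. All of this stands, and it confines the point to the binary score. A reader might infer that the primary outcome as a whole cannot register a device failure; the documents do not support that.

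A reader might also infer that such subjects are counted as successes. That is possible on the wording but weak: a subject who never reached the table has no value on either ground, and no section says that a missing value counts as success. Nor does the replacement rule in 2.8.1 define an analysis set; it governs the patient limit. It makes omission likely without prescribing it.

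It can further be said that an unending delay is the natural reading, so the score already works. The text does not exclude this, which is why the point concerns an unsettled rule and not a certain miss. If the sponsor intends that reading, it should be written down.

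Finally, the case needs several conditions together, and its frequency is unknown. Section 3.1 calls interrupted treatment unlikely, although it does not address a failure before delivery. This stands and lowers the severity.

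**Conclusion.** The point holds in a narrow form. The per-subject score in section 2.13 has no ground for device-related non-treatment with exit by business day 7 and at most an hour on the table. The most likely consequence is that the subject drops out of the score, so a device that treats late is marked down while one that does not treat may not be.

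The size cannot be estimated. The 91% against 100% for a single case assumes 10 treated successes, one such exit, and a summary proportion that the plan does not state. It should not be read as a finding that feasibility is overstated by 9 points. Field-size misfits and positive pregnancy tests are eligibility failures and do not belong in k. No decision rule or test is affected. Severity: minor; a cheap improvement.

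**What to change.** In section 2.13:

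1. Add a third NOT-feasible ground: FLASH treatment not delivered for a reason related to the investigational device, with the carve-out for patient and unrelated facility factors that the delay ground already has.
2. State that workflow feasibility is assessed in all eligible subjects who undergo CT simulation.
3. List every pre-treatment exit by the reason documented under 2.12, with field-size misfits and positive pregnancy tests on a separate line.
4. Base attribution on the documented exit reason and the device report under 2.10, and add a device-related yes/no item to the Subject End of Study form. No return-to-service date is needed.

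The limit of 10 treated subjects and the replacement rule stay as they are. Whether these cases also count toward a stopping rule is for the sponsor to decide.

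The cost is a short paragraph, one listing and one form item. The downside is that the feasibility figure may be slightly less favourable and some exits will need a judgement on attribution.
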